# 4.5. Duration of Treatment and End of Study Definition

[figure not shown]
Following a Screening Period of up to 28 days, there will be a Dosing and Follow up Period (single dose on Day 1 through the EOS Visit) of approximately 74 days.

Based on data from preclinical models, the half-life of ALXN1910 is expected to be approximately 7 days in healthy adult participants; therefore, the end of study visit is planned on Day 75, representing approximately 10 half-lives after initial study intervention administration. The total study duration per participant is approximately 103 days. An overview of the study visits is present in Figure 2.

A participant is considered to have completed the study if they complete all visits of the study including the last scheduled visit specified in the SoA (Section 1.3).

The end of the study is defined as the date the last participant completes the last visit (as specified in the SoA [Section 1.3]).

Figure 2: Overview of Study Visits

Abbreviation: D = day

#### 5. STUDY POPULATION

Prospective approval of protocol deviations to recruitment and enrollment criteria, also known as protocol waivers or exemptions, is not permitted.

#### 5.1. Inclusion Criteria

Participants are eligible to be included in the study only if all of the following criteria apply:

#### Age

1. Participants must be between 18 and 55 years of age (Japanese participants must be between 20 and 55 years of age), inclusive, at the time of signing the ICF.

#### Sex

2. Male or female, and willing to follow protocol-specified contraception guidance as specified in Section 10.7.

# **Type of Participant**

- 3. Participants who are healthy as determined by satisfactory medical assessment with no clinically significant or relevant abnormalities as determined by medical history, physical examination, vital signs, 12-lead ECG, and clinical laboratory evaluation (hematology, chemistry, coagulation, and urinalysis) that is reasonably likely to interfere with the participant's participation in or ability to complete the study, or to potentially confound interpretation of study results, as assessed by the Investigator.
- 4. Female participants must have a negative serum pregnancy test at Screening and negative urine pregnancy test on Day -1.
- 5. Participants of Japanese descent are defined as:
  - First generation (born to 2 Japanese parents and 4 Japanese grandparents).
  - Participant must have been born in Japan, and not have lived outside Japan for more than 10 years.
  - Lifestyle, including diet, must not have significantly changed since leaving Japan.

#### Weight

6. Body weight within 50 to 100 kg, inclusive, and body mass index within the range 18 to 29.9 kg/m², inclusive.

#### **Informed Consent**

7. Capable of giving signed informed consent as described in Section 10.1.3, which includes compliance with the requirements and restrictions listed in the ICF and in this protocol.

#### **5.2.** Exclusion Criteria

Participants are excluded from the study if any of the following criteria apply:

#### **Medical Conditions**

- 1. Current or recurrent disease (eg, cardiovascular, hematological, neurological, endocrine, immunological, rheumatological, renal, hepatic or gastrointestinal, or other conditions).
- 2. Current or relevant history of physical or psychiatric illness, use of prohibited therapies during the study, or make the participant unlikely to fully comply with the requirements of the study or complete the study, or any condition that presents undue risk from the study intervention or study procedures.
- 3. Any other significant disease or disorder that, in the opinion of the Investigator, may put the participant at risk.
- 4. Clinically significant abnormal vital signs at Screening or predose on Day 1. If vital signs are significantly abnormal, up to 2 additional readings will be taken. If neither of the 2 replicates are normal or non-significantly abnormal, the participant will be excluded from study participation. Blood pressure should be taken after a minimum of 5 minutes in supine position. Standing (orthostatic) blood pressure will also be performed at Screening only to exclude participants who are prone to orthostatic hypotension.
- 5. Clinically significant abnormal ECG at Screening or 12-lead ECG (triplicate) predose on Day 1. If ECG values are significantly abnormal, up to 2 additional triplicate ECGs will be performed. If neither of the 2 replicates are normal or non-significantly abnormal, the participant will be excluded from study participation.
- 6. History of malignancy, apart from nonmelanoma skin cancer or carcinoma in situ of the cervix, that has been treated with no evidence of recurrence within 5 years.
- 7. HIV infection (evidenced by HIV-1 or HIV-2 antibody titer).
- 8. Acute or chronic hepatitis B virus infection (evidenced by positive hepatitis B surface antigen [HBsAg] or positive core antibody [HBcAb] with negative surface antibody [HBsAb]) at Screening will not be enrolled.
- 9. Acute or chronic hepatitis C virus infection (evidenced by antibody titer).
- 10. History of significant allergic reaction (eg, anaphylaxis or angioedema) to any product (eg, food, pharmaceutical).

# **Prior/Concomitant Therapy**

- 11. Use or intended use of prescription medications (excluding oral contraceptives and paracetamol/acetaminophen at doses ≤ 3000 mg per day) within 14 days or 5 half-lives of the drug (whichever is longer) prior to Day -7, and/or intended use at any point over the duration of the study except with prior approval of Alexion.
- 12. Use of nonprescription/over-the-counter medications (excluding paracetamol/acetaminophen at doses  $\leq$  3000 mg per day), including herbal remedies and supplements, within 7 days to dosing Day 1, except with prior approval of Alexion.

13. Use of vitamin B6 (including vitamin supplements that contain vitamin B6) for at least 2 weeks prior to Screening.

# **Prior/Concurrent Clinical Study Experience**

14. Current enrollment or past participation, within the last 90 days, before signing of consent in this or any other clinical study involving an investigational study intervention. Participants, involved in intervention studies using investigation or non-investigational drug with prolonged half-lives, are not eligible unless the time since last treatment has exceeded 90 days or 5 half-lives of the study intervention, whichever is longer.

### **Diagnostic Assessments**

- 15. Presence of fever (confirmed body temperature > 37.6°C) (eg, a fever associated with a symptomatic viral or bacterial infection) within 14 days prior to dosing on Day 1.
- 16. Alkaline phosphatase greater than the ULN or lower than the lower limit of normal of the reference range of the testing laboratory at Screening or on Day -1.
- 17. Serum creatinine greater than the ULN of the laboratory reference range at Screening or on Day -1; estimated glomerular filtration rate < 90 mL/min/1.73 m^2.
- 18. ALT or aspartate aminotransferase > ULN of the reference range of the testing laboratory at Screening or on Day -1.
- 19. Any clinically significant abnormal hematological parameters (per the Investigator's discretion).
- 20. Positive urine drug toxicology screen at Screening or on Day -1.
- 21. Positive urine alcohol test at Screening or Day -1
- 22. Donation of plasma within 7 days prior to dosing; donation or loss of blood (excluding volume drawn at Screening) of more than 50 mL within 30 days of dosing on Day 1, or more than 499 mL of blood within 56 days of dosing on Day 1.

#### **Other Exclusions**

- 23. Female participants who are pregnant or breastfeeding.
- 24. Major surgery or hospitalization within 90 days prior to dosing on Day 1.
- 25. History of exposure to asfotase alfa.
- 26. History of allergy or hypersensitivity to excipients of asfotase alfa or ALXN1910 (eg, sodium phosphate, sodium chloride).
- 27. Use of tobacco in any form (eg, smoking or chewing) or other nicotine-containing products in any form (eg, gum, patch, electronic cigarettes) from 2 hours before admission through discharge from the CRU, for both inpatient and outpatient visits. (Former smokers may be permitted to enroll at the Investigator's discretion).
- 28. History of illicit drug abuse, history of alcohol abuse within 1 year prior to Screening, or clinical evidence of substance and/or alcohol abuse within the 2 years before Screening. Alcohol abuse is defined as regular weekly intake of more than 14 units for both men and women (https://www.nhs.uk/conditions/alcohol-misuse/).

# 5.3. Justification for Study Population

This is the first time that ALXN1910 will be administered to humans. Alexion considers that healthy participants are the appropriate population for this study, as they will enable PK and safety assessments without the potential of confounding effects due to other disease activity, comorbidities, or medications. Based on the available nonclinical data with ALXN1910, the sequential cohort study design with SAD administration of ALXN1910 IV or SC are expected to adequately assess safety, tolerability, and PK, and allow flexibility to change the injected dose as clinical data are generated.

The inclusion of a cohort of Japanese participants will meet regulatory requirements of the ICH Guidance E5(R1) and Japan Ministry of Health, Labour and Welfare guidance on Basic Principles on Global Clinical Trials. The ICH E5 guideline provides a general framework for evaluating the potential impact of ethnic factors on the acceptability of foreign clinical data, with the underlying objective of minimizing duplication of clinical data, and it also describes the requirement of bridging studies for extrapolation of foreign clinical data to a new region (ie, Japan).

# 5.4. Lifestyle Considerations

### **5.4.1.** Meals and Dietary Restrictions

- Participants are required to abstain from ingesting food containing poppy seeds within 24 hours prior to admission to the CRU.
- No outside food or drink is permitted at the CRU. All meals and snacks will be provided. Participants will receive standard meals and snacks at scheduled times during confinement.

#### 5.4.2. Activity

Participants will be required to remain in supine position for dosing and for approximately 15 minutes after study intervention administration. Vigorous activity will be prohibited at all times throughout confinement at the CRU.

#### 5.4.3. Caffeine, Alcohol, and Tobacco

Participants will be required to abstain from the following:

- Ingesting caffeine- or xanthine-containing products (eg, coffee, tea, cola drinks, and chocolate) 24 hours before admission through discharge from the CRU and 24 hours before each outpatient visit.
- Ingesting alcohol 24 hours before admission through discharge from the CRU and 24 hours before each outpatient visit.
- Smoking nicotine or use of tobacco products from 2 hours before admission through discharge from the CRU.

#### 5.5. Screen Failures

Screen failures are defined as participants who consent to participate in the clinical study but are not subsequently randomly assigned to study intervention/entered in the study. A minimal set of screen failure information is required to ensure transparent reporting of screen failure participants to meet the Consolidated Standards of Reporting Trials publishing requirements and to respond to queries from regulatory authorities. Minimal information includes demography, screen failure details (eg, failed eligibility criteria), and any AEs, including any SAEs and any related concomitant medication, occurring during the Screening Period.

Individuals who do not meet the criteria for participation in this study (screen failure) due to a reason that is expected to resolve or has resolved, may be rescreened based on discussion and agreement between the Investigator and the Medical Monitor. Rescreened participants are required to sign a new ICF.

#### 6. STUDY INTERVENTION

Study intervention is defined as any investigational intervention(s), marketed product(s), placebo, or medical device(s) intended to be administered to a study participant according to the study protocol.

# 6.1. Study Interventions Administered

The study intervention composition and doses to be administered in this study are presented in Table 7.

Table 7: Dose Reference Chart for Study ALXN1910-HV-101

Study Intervention Name	ALXN1910 IV	ALXN1910 SC	Placebo
Туре	Biologic	Biologic	Placebo
Dose Formulation	ALXN1910 is formulated at pH 7.3 and each vial contains 100 mg of ALXN1910 in 10 mM sodium phosphate, 70 mM glycine, 210 mM sucrose, and 0.05% PS80.	ALXN1910 is formulated at pH 7.3 and each vial contains 100 mg of ALXN1910 in 10 mM sodium phosphate, 70 mM glycine, 210 mM sucrose, and 0.05% PS80	0.9% normal saline
Unit Dose Strength(s)/Dosage Level(s)	5 and 15 mg, single-dose	15, 45, and 135 mg, single-dose	0 mg, single-dose
Route of Administration	IV infusion	SC injection	IV infusion or SC injection
Use	Experimental	Experimental	Placebo
IMP and NIMP	IMP	IMP	IMP

Abbreviations: IMP = investigational medicinal product; IV = intravenous; NIMP = non-investigational medicinal product; PS80 = polysorbate 80; SC = subcutaneous

#### 6.1.1. Study Intervention Packaging and Labeling

At minimum, bulk ALXN1910 vials supplied by Alexion will be labeled with:

- A. Protocol number
- B. Lot number/expiry date
- C. Alexion name and address
- D. Instructions for use and storage

ALXN1910 will be labeled according to the country's regulatory requirements. All packaging and labeling operations will be performed according to GMP and relevant regulatory requirements. Participant doses prepared by the site will be QP certified and released by the CRU.

# 6.2. Preparation/Handling/Storage/Accountability

Details regarding preparation, handling, storage, accountability, and administration of the study intervention are discussed below.

- The Investigator or designee must confirm appropriate temperature conditions have been maintained during transit for all study intervention received and that any discrepancies are reported and resolved before use of the study intervention.
  - Only participants enrolled in the study may receive the study intervention and only authorized site staff may supply or administer the study intervention. All study intervention must be stored in a secure, environmentally controlled, and monitored (manual or automated) area in accordance with the labeled storage conditions with access limited to the Investigator and authorized site staff.
  - The Investigator (or designee), institution, or the head of the medical institution (where applicable) is responsible for study intervention accountability, reconciliation, and record maintenance (ie, receipt, reconciliation, and final disposition records).
  - This responsibility includes the reporting of any temperature excursions and product complaints to [contact] and [contact] within 1 business day of awareness. A product complaint is defined as any written, electronic, or oral communication that alleges deficiencies related to the identity, quality, durability, reliability, usability, safety, effectiveness, or performance of a product or clinical study material and/or its packaging components after it is has been released for distribution to an end customer that affects the performance of such product.

Further guidance regarding preparation, handling, storage, and accountability and information for the final disposition of unused study intervention is provided in the pharmacy manual.

# 6.3. Measures to Minimize Bias: Randomization and Blinding

Up to approximately 48 participants will be randomized according to a randomization schedule generated prior to the start of the study. The participants in each dose cohort will be randomized in a 3:1 ratio to receive ALXN1910 or placebo.

The randomization codes will be maintained in a location with access restricted to pharmacy personnel only. Once a randomization number has been assigned to a participant, it may not be assigned to another participant.

This is a double-blind study. Participants and on-site medical/nursing staff at the study site will be blinded to study intervention/dose assignment. The pharmacy staff preparing the investigational products will not be blinded to study intervention/dose assignment, but all other site staff, including the Investigator, will be blinded.

As the treatment with ALXN1910 can cause increases in serum ALP, knowledge of the ALP results could jeopardize the double-blind design of the study. Therefore, ALP results for the post-dose time points will not be available to review by the Investigator; however, the ALP results will be available in a blinded manner for each cohort at the time of SRC meeting.

Alexion staff will be unblinded only when necessary (eg, to monitor that SC/IV dosing are being prepared appropriately, to determine reportability of SAEs for dose escalation decisions) and will refrain from sharing any information on study intervention assignment with the study center staff or others at Alexion, especially with regard to assessment and reporting of safety.

The study intervention assignment to each participant will be provided to the Investigator. This information will be retained by the Investigator (or representative) in a secured manner. In case of an emergency, the Investigator has the sole responsibility for determining if unblinding of a participants' intervention assignment is warranted. Participant safety must always be the first consideration in making such a determination. If the Investigator decides that unblinding is warranted, the Investigator should contact Alexion prior to unblinding a participant's intervention assignment unless this could delay emergency treatment for that participant. If a participant's intervention assignment is unblinded, Alexion must be notified within 24 hours after breaking the blind.

Additional details regarding the blinding/unblinding process (including masking techniques) will be included in the pharmacy manual.

As emerging PK and safety data from each cohort of this study will be needed for timely decisions about adjustments of doses or escalate dosing in subsequent cohorts, the emerging data will be unblinded for analysis. An independent unblinded team that is limited to key stakeholders will perform unblinded PK analyses and prepare preliminary summaries of PK and safety data as needed before data are more generally unblinded. These summaries will not reveal individual participant's treatment assignments. Except as noted above, other members of the study team will remain blinded.

## **6.4.** Study Intervention Compliance

Participants will receive study intervention directly from the Investigator or designee, under medical supervision. Dosing date and time will be recorded in the source documents and recorded in the eCRFs. The dose of study intervention and study participant identification will be confirmed at the time of dosing by a study site personnel other than the person administering the study intervention.

# **6.5.** Concomitant Therapy

Any medication (including over-the-counter or prescription medicines, vitamins, and/or herbal supplements), vaccine, or other specific categories of interest that the participant is receiving from 14 days prior to the dose of study intervention until the EOS Visit must be recorded along with:

- Reason for use
- Dates of administration including start and end dates
- Dosage information including dose and frequency

The Medical Monitor should be contacted if there are any questions regarding concomitant or prior therapy.

### 6.5.1. Allowed Medicine and Therapy

• Paracetamol/acetaminophen at doses of a maximum 3000 mg per day is permitted for use as an exception with the approval of the Investigator.

- Concomitant procedures are not allowed unless medically indicated and/or permitted by Alexion or the Investigator or designee.
- Concomitant medications may be used during the study if deemed medically indicated by the Investigator. The Investigator or designee will notify Alexion of any AEs requiring administration of prescription medication(s) while on study.

## 6.5.2. Disallowed Medicine and Therapy

- Participants must abstain from taking prescription or non-prescription drugs
  (including vitamins and dietary or herbal supplements) within 7 days (or 14 days if
  the drug is a potential enzyme inducer) or 5 half-lives (whichever is longer) before
  the start of study intervention until completion of the EOS Visit, unless, in the
  opinion of the Investigator and Alexion, the medication will not interfere with the
  study.
- Participants must abstain from taking prescription medications within 21 days or 5 half-lives (whichever is longer) of Day -1 or non-prescription drugs (including vitamins and dietary or herbal supplements) within 7 days or 5 half-lives (whichever is longer) before Day -1 and until completion of the EOS Visit.

## 6.6. Dose Modification

Decisions to continue or modify dosing will be made by the Investigator and/or SRC after review of the blinded data as described in Table 8. The SRC may also make recommendations regarding safety issues, study conduct, or study suspension.

Predicted ALXN1910 human PK exposure (Table 6) indicates Cohort 5 or Cohort 6 mean projected PK exposure should not exceed 50% of the NOAEL exposure established in the 28-day GLP toxicology study in monkeys. In the event that mean PK exposure in Cohort 5 or Cohort 6 is predicted to exceed 50% of the NOAEL exposure, a lower dose will be selected so the above criteria can be met. PK data will not be used for dose escalation from Cohort 1 to Cohort 2 as greater than 150-fold PK (safety) exposure margin is expected for Cohort 2.

Dose escalation requires agreement between the Investigator and Alexion; Alexion may not supersede the Investigator if there are concerns that dosing should be stopped.

**Table 8:** Detailed Dose Escalation Criteria for Each Cohort

Dosing Decision	Responsible Party	Data to be Reviewed	Documentation/ Communication Methods
Dose escalation from Cohort 1 to Cohort 2	SRC	• At minimum, 14 days of postdose safety and tolerability data from at least 7 participants in Cohort 1.	The SRC will document the decision on the escalation/progression approval form.
Dose escalation from Cohort 2 to Cohort 5 (in parallel with Cohort 3 and Cohort 4)	SRC	
 
At minimum, 14 days of postdose safety and tolerability data from at least 7 participants in Cohort 2.
 
Seven days of PK data from at least 7 participants in Cohort 1 and at least 7 participants in Cohort 2.
 
	The SRC will document the decision on the escalation/progression approval form.
Dose escalation from Cohort 5 to Cohort 6	SRC	
 
At minimum, 14 days of postdose safety and tolerability data from at least 7 participants in Cohort 5.
 
Seven days of PK data from at least 7 participants in Cohort 5.
 
The cumulative PK data from Cohort 1 and Cohort 2.
 
	The SRC will document the decision on the escalation/progression approval form.

Abbreviations: PK = pharmacokinetic; SRC = Safety Review Committee

# 6.7. Intervention After the End of the Study

This is a healthy participant study. No follow-up ALXN1910 administration is planned.

# 7. DISCONTINUATION OF STUDY INTERVENTION AND PARTICIPANT DISCONTINUATION/WITHDRAWAL

## 7.1. Discontinuation of Study Intervention

Although not anticipated for this study, if an acute infusion reaction occurs during IV infusion dosing, the research clinic should follow the steps outlined in the Acute Infusion Reaction Algorithm (Section 10.5). Participants who are unable to complete their IV dose on Day 1 should complete the scheduled safety assessments, if possible, but another participant must be enrolled.

## 7.2. Cohort Stopping Rules

In the event an acute safety event occurs in any cohort, dosing should be stopped until a causality assessment has taken place and an appropriate risk mitigation strategy is put into place before dosing the remainder of the cohort.

Assessment of AE intensity/severity should be performed by the Investigator using clinical judgment and according to criteria from NCI CTCAE version 5.0, published 27 Nov 2017 (see Section 10.3.3). As CTCAE grading is intended for oncology patients, study-specific modifications related to the liver, hematology, and QT interval prolongation have been made to ensure clear guidance and appropriate grading of AEs for this study in healthy participants (Table 11).

If a cohort stopping rule (Table 11) is met, no further dosing at the dose level or higher will proceed. Continuation of the cohort and/or study will require a substantial protocol amendment.

Unless a cohort stopping rule is met, dose continuation or escalation will proceed as scheduled and the study will continue as planned provided no prespecified toxicity events occur (as determined by the SRC).

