A blinded SRC, consisting of the Investigator, Medical Monitor, Drug Safety Physician, Study Statistician, and Clinical Pharmacologist will evaluate the available study data at prespecified time points for participant safety and make recommendations on dose escalation, dose modification, or termination of the study. Decisions to continue, modify (explore the dose cohort further), or escalate dosing will be made by the Investigator and/or SRC as described in Section 4.1 and Section 7.

The SC and IV doses to be studied in healthy participants in this study are predicted to be within the PK/safety exposure margins established from a 28-day toxicology study in monkeys.

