## 10.3.4. Reporting of SAEs

#### SAE Reporting to Alexion or Delegate via Paper Safety Reporting Form

- All SAEs will be recorded and reported to Alexion or designee immediately and within 24 hours awareness.
- SAEs will be reported using the Safety Reporting Form and submitted to Alexion GDS. The Investigator
  must complete, sign, and date the SAE pages, verify the accuracy of the information recorded on the SAE
  pages with the corresponding source documents, and send a copy via email or facsimile to the contact
  information provided below:
  - Email: [contact] or Fax: [name]
- Additional follow-up information, if required or available, should be entered into the eCRF and sent to
  Alexion GDS within 24 hours of the Investigator or study site staff becoming aware of this additional
  information via the reporting process outlined above.
- For all SAEs, the Investigator must provide the following:
  - Appropriate and requested follow-up information in the time frame detailed above
  - Causality of the SAE(s)
  - Treatment of/intervention for the SAE(s)
  - Outcome of the SAE(s)
  - Medical records and laboratory/diagnostic information
- All paper forms and follow-up information submitted to Alexion GDS **must** be accompanied by a cover page signed by the Investigator.
- Paper source documents and/or reports should be kept in the appropriate section of the study file.

Abbreviations: AE = adverse event; ALT = alanine aminotransferase; AST = aspartate aminotransferase; eCRF = electronic case report form; CTCAE = Common Terminology Criteria for Adverse Events; ECG = electrocardiogram; GDS = Global Drug Safety; Hb = hemoglobin; SAE = serious adverse event; ULN = upper limit of normal.

**Table 11:** Cohort and Study Stopping Rules

Adverse Events Related to Study Intervention	Showing Signs of Reversibility	Number of Participants	Action
	 	-	~ 1 ~ 5 !
Moderate (CTCAE Grade 2)	Yes	$\geq 3$ in 1 SOC	Cohort: Dosing of the
		$\geq$ 4 total in	remainder of the
	NT.	different SOCs	cohort suspended
	No	$\geq 2$ total in	Study: Dosing of
T ' ' ' ' ' C ' ' ' ' ' ' '	NI o	different SOCs	equal or higher doses
Injection/infusion site reactions:	Noa	≥ 3	suspended
Moderate (CTCAE Grade 2)			Dosing of lower dose
			levels can continue
Injection/infersion related recetions (including	Noa	≥ 3	Continuation of
Injection/infusion related reactions (including hypersensitivity):	No	≥ 3	dosing of equal or
Moderate (CTCAE Grade 2)			higher doses requires

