Woderate (CTCAE Grade 2)			a substantial
QT interval prolongation:	NA	≥ 2	amendment d
A prolongation of the uncorrected QT interval	11/1		
of greater than 500 msec, using consistent,			
technically valid triplicate ECG (CTCAE			
Grade 2)			
Hematology (CTCAE Grade 2):	NA	≥ 2	
Hb drop to absolute values of < 10g/dL (100			
g/L)			
Platelet count drop to absolute values of <			
75,000/mm 			
Severe (CTCAE Grade 3)	NA	2	Study suspended (all
Or			dosing [lower, equal,
Serious AE (not fatal or life-threatening)			or higher doses]
Or			suspended)
Hy's law:			
ALT or AST value $> 3 \times ULN$ together with			Continuation of the
bilirubin increase $> 2 \times ULN$ , without other			cohort or study
evidence of cholestasis (CTCAE Grade 3)			requires a substantial
Or			amendment b
ALT or AST value > 8 × ULN.			
ALT or AST value > 3 × ULN, and			
symptomatic (CTCAE Grade 3) Or			
Injection/infusion site reactions:			
Severe (CTCAE Grade 3)			
Or			
Injection/infusion related reactions (including			
hypersensitivity):			
Severe (CTCAE Grade 3)			
Or			
Hematology (CTCAE Grade 3):			
Hb drop to absolute values of $\leq 8 \text{ g/dL}$			
Serious (fatal or life-threatening, CTCAE	NA	1	
Grades 4 and 5)			

<sup>a For injection/infusion site reactions, a cohort and/or the study will be suspended when ≥ 3 participants are observed. If all but 1 affected participant show signs of recovery (at least to Grade 1), cohort and study continuation can then proceed. If ≥ 2 participants remain at Grade 2 after the minimum data review period, the period of observation should be extended for up to 168 hours. If all but 1 affected participant show sign of

recovery (at least to Grade 1), cohort and study continuation can then proceed. If  $\geq 2$  affected participants remain at Grade 2 after the first 168-hour extension period, the SRC will make the decision to either prolong further the observation period up to a maximum of another 168 hours or suspend the remainder of the cohort and study. At the end of the second extension period, if all but 1 participant show sign of recovery (at least to Grade 1), cohort and study continuation can then proceed. If, however,  $\geq 2$  affected participants remain at Grade 2, cohort and study will be suspended.

b A substantial amendment may include an amendment to the protocol, the ICF, or other study-related documents as appropriate.

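### Section 7.2 restates the effect of meeting a Table 11 stopping rule more narrowly than Table 11's severe block, which stops dosing at every level

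*Protocol*

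**What the plan says.** Protocol Section 7.2 states the effect of a rule in its third paragraph: "If a cohort stopping rule (Table 11) is met, no further dosing at the dose level or higher will proceed". The next sentence requires a substantial protocol amendment before the cohort and/or study continues. The last paragraph opens "Unless a cohort stopping rule is met, dose continuation or escalation will proceed as scheduled" and adds a second condition, that no prespecified toxicity has occurred in the SRC's judgment. The second paragraph explains the grading and says that "study-specific modifications related to the liver, hematology, and QT interval prolongation have been made", with a reference to Table 11.

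Table 11 (after Section 10.3.4) is titled "Cohort and Study Stopping Rules" and has two levels of action.

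- **Grade 2 block.** The rest of the cohort is suspended. A study-level line beginning "Study: Dosing of" suspends equal and higher doses. A further line beginning "Dosing of lower dose" lets lower levels go on. An amendment is needed to resume equal or higher doses. For injection and infusion reactions, footnote a lets the cohort and study continue once all but one affected participant is recovering.
- **Severe block.** This covers related Grade 3 events, non-fatal serious events, Hy's law and ALT/AST criteria, Grade 3 site or infusion reactions and Grade 3 hematology, with a trigger of 2 participants. The action begins "Study suspended (all" and goes on to list lower, equal and higher doses. Continuing the cohort or study needs an amendment.

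The fatal or life-threatening row (trigger: 1 participant) follows directly, with no action text of its own in the text available to us.

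Section 2.4.3 says that decisions to continue, modify or escalate dosing "will be made by the Investigator and/or SRC as described in Section 4.1 and Section 7".

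**The concern.** The body text and the table give different scopes for the same event. For a severe-block trigger, Section 7.2 names only the current dose level and those above it, while Table 11 stops everything. The last paragraph of Section 7.2 then makes scheduled dosing depend on a cohort stopping rule and does not name study rules, although Table 11 contains both.

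This would be academic if cohorts ran strictly one after another at rising doses. They do not. Under footnote a of Table 5, the 15 mg Cohorts 3 (IV) and 4 (SC, Japanese participants) may run alongside the 45 mg SC Cohort 5. A lower dose level can therefore be open when a rule is met at a higher one. In a first-in-human trial, the text that governs the gravest triggers should have one reading.

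**Working it through.** No planned figure has to be reproduced. The check compares the texts and then counts who could be affected.

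**Step 1: dosing consequence, side by side**

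| Trigger | Section 7.2 | Table 11 | Match on doses stopped? |
|---|---|---|---|
| Grade 2 block | same level and higher stop | equal and higher stop; lower may continue | yes |
| Severe block, 2 participants | same level and higher stop | lower, equal and higher all stop | no, 7.2 is narrower |
| Fatal or life-threatening, 1 participant | same level and higher stop | appears to share the severe action (from position) | no, if that inference is right |

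**Step 2: amendment requirement.** Here Section 7.2 errs the other way. Its amendment sentence covers any Table 11 rule and the cohort and/or study as a whole. In the Grade 2 block, Table 11 lets lower doses continue without an amendment, and footnote a allows continuation after recovery. A correction therefore has to deal with both sentences of the third paragraph.

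**Step 3: which cohorts count as lower?** Predicted values from Table 6:

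| Cohort | Dose | Cmax (μg/mL) | AUC to 168 h (h × μg/mL) |
|---|---|---|---|
| 3 | 15 mg IV | 3.4 | 225.1 |
| 4 | 15 mg SC | 1.3 | 153.6 |
| 5 | 45 mg SC | 3.3 | 398.2 |
| 6 | 135 mg SC | 10.2 | 1208.8 |

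- Cohort 4 against Cohort 5: Cmax 1.3/3.3 = 0.39; AUC 153.6/398.2 = 0.39. Lower on every measure.
- Cohort 3 against Cohort 5: Cmax 3.4/3.3 = 1.03; AUC 225.1/398.2 = 0.57. Lower in mg and AUC, but not in predicted Cmax.
- Against Cohort 6: Cohort 3 Cmax 3.4/10.2 = 0.33 and AUC 225.1/1208.8 = 0.19; Cohort 4 Cmax 1.3/10.2 = 0.13 and AUC 153.6/1208.8 = 0.13. Both lower on every measure.

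Cohort 6 is relevant because Table 8 does not require Cohorts 3 or 4 to be complete before escalation from Cohort 5 to Cohort 6.

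**Step 4: undosed participants.** Each cohort has 8 at 3:1, so 6 active and 2 placebo. The sentinel pair is 1 active and 1 placebo, and up to 3 more follow before the remainder (Section 4.1).

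| Stage when the rule is met | Undosed per cohort | Cohorts 3 + 4, same stage |
|---|---|---|
| Not started | 8 (6 active) | 16 (12 active) |
| After sentinel pair | 8 − 2 = 6 (5 active) | 12 (10 active) |
| After sentinel pair + 3 | 8 − 5 = 3 (2 to 3 active) | 6 (4 to 6 active) |
| Complete | 0 | 0 |

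The range is 0 to 8 for Cohort 4 alone and 0 to 16 with Cohort 3, or up to 16/48 = 33.3% of the planned sample. Replacements under Sections 7.1 and 7.3 are not counted.

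**The case against.** The strongest reply is that Section 7.2 is incomplete rather than contradictory. Stopping the current level and above is part of stopping everything, and nobody can decide that a rule is met without opening Table 11, where trigger and action sit together. The amendment sentence in Section 7.2, repeated in general terms in Section 9.6, would itself stand in the way of dosing Cohorts 3 or 4 after a severe-block event, since that would be continuing the study. Section 7.2 also opens with a stop after an acute safety event in any cohort, and under Section 6.6 the sponsor cannot override an Investigator who has concerns that dosing should stop. All of this stands and keeps the risk low.

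It can also be said that a cohort stopping rule means only the cohort-level rows. The section heading supports this, and the wording tracks the Grade 2 action. The reading is possible but weak. Section 7.2 cites Table 11 without limiting it to a block. It mentions the liver modifications, which appear only in the severe block, although that mention concerns grading. The Grade 2 block itself carries both a cohort and a study action, so the table does not divide cleanly. If the reading were right, Section 7.2 would state no dosing effect for the study-level rules. The prespecified-toxicity condition in the last paragraph could be meant to cover them, but it does not say so.

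A reader might infer that the protocol lets lower-dose cohorts carry on after severe or fatal events. The documents do not support that: Section 7.2 is silent on lower doses, and Table 11 expressly stops them in the severe block.

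**Conclusion.** Section 7.2 and Table 11 state different scopes for a severe-block stop, in current text. This is a low-risk inconsistency in a safety rule, not a missing safeguard: Table 11 is explicit and more conservative, and Section 7.2 leads to it. It should still be corrected, because Section 2.4.3 sends dosing decisions to Section 7 and the narrower wording covers the most serious triggers.

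The practical exposure is confined mainly to the 15 mg Cohorts 3 or 4 still being dosed when a severe-block rule is met at 45 mg or 135 mg. The 0 to 16 range is a count of cohort places at each stage of dosing. It carries no probability and should not be read as expected exposure or harm. At 45 mg, including Cohort 3 assumes that dose level is read in mg. The action for the fatal or life-threatening row rests on its position in the table.

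**What to change.** Replace both sentences of the third paragraph of Section 7.2 with:

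*If any stopping rule in Table 11 is met, the action in the Table 11 Action column for that rule, including its footnotes and its requirement for a substantial amendment, will be taken; where that action is study suspension, all dosing at lower, equal and higher doses stops.*

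In the last paragraph, extend the opening condition to *a cohort or study stopping rule*.

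Replacing both sentences matters. Leaving the blanket amendment sentence would keep a conflict with footnote a and with lower doses continuing in the Grade 2 block.

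The cost is one paragraph and one phrase in a protocol amendment. Table 11, its triggers and footnotes, the sample size and the analysis do not change.
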